9.1.2. Planned analyses and statistical methodology to be used

We will employ "Intention-to-Treat" (ITT) principles. Statistical tests will be performed based on a two-sided test at the 5% level of significance. Supporting analyses will also be performed. A "per protocol" analysis will restrict the analysis to participants who receive minimal exposure to the intervention, have a minimal number of longitudinal evaluations, and/or are free of major protocol violations. A "completer" analysis will only include participants who completed acute treatment without exiting or prematurely terminating from their assigned treatment. Because participants may be removed differentially across the treatment arms in these analyses, both approaches are vulnerable to differential selection bias and will be interpreted cautiously.

Most of the study outcomes are observed repeatedly at well-defined time-points postrandomization, so that statistical methods for repeated measures data will be applied. This includes the linear model with structured covariance matrices and the mixed effects models as implemented in PROC MIXED in SAS. Site will also be included as an independent variable in order to account for variability among the study sites.

Covariates in Regression Models: The baseline value of the outcome, centered about its sample mean, will be included in each analysis. Otherwise, only age and sex will be entered as covariates.

Missing Values: We will proactively monitor the amount of missing data, and ensure that we respond quickly to emerging problems. Statistically, missing data will be addressed through the use of mixed models analysis which will be carried out with PROC MIXED in SAS. We will carry out an assessment of the degree to which the structured covariance matrix in mixed effects models fits the data.

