fMRI Analysis: The monetary incentive delay task entails three key task phases: anticipating making a response, anticipating an outcome, and receiving that outcome. Functional brain responses to these three task phases will be identified using a General Linear Model based statistical analyses (GLM). Here, a statistical test is carried out between the actual data (fMRI time series) and a predicted model (event timings and parametric modulations by behavior). If the fit between the predicted and actual data is good, then a relationship is concluded to exist between the actual data (voxel intensity values) and task-related factors (anticipation, response, receipt). Having tested the fit at the single subject level for each experimental session, the data will be combined into a second-level, random-effects, repeated-measures analysis of variance. Statistical inferences about task effects will be made after appropriate correction for multiple comparisons. Regions of interest or ROIs will be defined with reference to a standard brain atlas (that of Talaraich and Tournoux). The fMRI primary analysis (see below) will focus on the ventral striatum. However, exploratory analyses will be carried out with other ROIs. Cluster-wise parameter estimates for each condition (anticipation, response, receipt) will be extracted for the ventral striatum (and from the other predefined ROIs for exploratory analysis) and correlated with receptor occupancies. In this manner our regression analyses will be robust to non-independence error.

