9.1.2.1. Primary Analysis

Point estimate and the corresponding confidence interval for the primary study outcome (fMRI ventral striatal activation during reward anticipation of reward during the MID) of

the adjusted predicted score will be obtained. A mixed effects model analysis will be carried out for the primary outcome of the study, task-related fMRI activation in the ventral striatum during anticipation of reward occurring during the Monetary Incentive Delay Task. This analysis will test the hypothesis that CERC-501 will lead to a greater increase in ventral striatal activation during anticipation of reward than placebo.

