9.2. Power Analysis

A total of 90 subjects will be randomized: 45 subjects randomized to CERC-501 and 45 to placebo and included in the primary efficacy analysis. We conservatively anticipate that we will have incomplete data on up to 20% of subjects due to subject drop out or loss of data due to factors such as poor scan quality. As a result, we estimate that we will have complete data on as few as 72 subjects and as many as 90 subjects. In the section above, we outline how we will address the issue of missing data including carrying out analyses on the intent-to-treat (ITT) population and employing mixed effect models. If we assume the worst case scenario of 72 subjects, for a one tailed t-test at an alpha value of 0.05, power is 80% to identify an effect size of 0.58. For a one tailed t-test at an alpha value of 0.10 power is 80% to identify an effect size of 0.50. In Figure 4, it is indicated the effect that could be detected with 80% power at the alpha=0.05 level as a function of number of subjects.

Our capacity to estimate the expected effect size on our primary outcome measure is limited by the studies that have been carried out with this measure to date. The most relevant study was carried out by Stoy and co-workers (2011) who evaluated 15 patients with major depression and 15 controls and administered open-label escitalopram to both groups for 6 weeks and assessed outcome with fMRI activation of the ventral striatum during the MID. However, it must be kept in mind that estimates of power based on this study are likely overly optimistic because this was an open-label treatment study and only included 15 depressed subjects. We can estimate the expected effect size for our study from the ventral striatal activation to reward anticipation subject group by time interaction observed in this study. The effect size for a greater increase in those with depression compared with controls is 0.88. We can also estimate effect size from the pre-

to-post treatment difference in ventral striatal activation during reward anticipation and reward during the MID with fMRI within the depressed group which are 1.1 and 1.0 respectively. These effect sizes suggest that we are likely to have more than sufficient power to detect a significant effect with our primary outcome measure in the proposed study at the alpha=0.05 level with 80% power.

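### Primary fMRI endpoint: intention-to-treat plus a mixed model cannot bring in subjects without a Week 8 scan, so the planned analysis is an on-treatment analysis of scanned subjects and should be labelled and stress-tested as one

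*Protocol*

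**What the plan says.** Protocol 9.1.2 adopts intention-to-treat principles. It justifies repeated-measures methods on the ground that "Most of the study outcomes are observed repeatedly at well-defined time-points postrandomization". On covariates it says "The baseline value of the outcome, centered about its sample mean, will be included in each analysis", with age and sex added and site as a further term. On missing values it says "Statistically, missing data will be addressed through the use of mixed models analysis which will be carried out with PROC MIXED in SAS".

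Section 9.1.2.1 applies this to the primary endpoint: "A mixed effects model analysis will be carried out for the primary outcome of the study". The fMRI paragraph of 9.1.2 also describes a group-level step in which "the data will be combined into a second-level, random-effects, repeated-measures analysis of variance".

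Section 9.2 expects incomplete data on up to 20% of subjects "due to subject drop out or loss of data due to factors such as poor scan quality". It answers by pointing back to the plan to "address the issue of missing data including carrying out analyses on the intent-to-treat (ITT) population and employing mixed effect models", and it describes the 90 as "45 subjects randomized to CERC-501 and 45 to placebo and included in the primary efficacy analysis".

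The design of the endpoint is set elsewhere. Section 8.4.1 schedules the task fMRI at Day 0 and after 8 weeks of treatment only. A footnote to Table 3 says the second scan is not done in subjects who come off drug before Week 8. Section 4.5 omits fMRI from the early-withdrawal evaluation and says that withdrawals are not replaced. Sections 7.2 and 8.4.4.3 remove subjects whose CGI-I exceeds 5.

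**The concern.** A mixed model helps with dropout when a subject who leaves has already given some post-baseline values of the outcome. That is so for SHAPS, measured at Weeks 2, 4, 6 and 8. It is not so for the primary endpoint, which has one post-baseline value that is missing by design after early stopping. The plan thus claims for its primary analysis a property that the design does not supply.

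The analysis will in fact rest on nearly the same subjects as the completer analysis. Section 9.1.2 itself warns that the completer analysis is open to differential selection bias, but the primary analysis carries the intention-to-treat label and no such warning. Section 1.2.2 treats failure on this circuitry as reasonable grounds to abandon the mechanism, so readers need to know which subjects and which effect the result describes, and how far it depends on lost scans.

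**Working it through.** **The plan's own figure.** 90 × (1 − 0.20) = 72, or 36 per arm. At an effect size of 0.58, one-sided 5%, power is 79.3% (normal) or 78.6% (t). The stated 80% at 72 reproduces. It is already computed on subjects with complete data, so it stands.

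**Which subjects inform the estimate.**
- Baseline as covariate (9.1.2 and 9.1.2.1): a subject without a Week 8 scan has no outcome row. In a simulated trial of 90 with 18 scans missing, the model used 72 rows and gave the same estimate as the 72 alone.
- Baseline as a response with a common baseline mean: in a second simulated set (90 randomised, 65 scanned) the estimate was 0.4929 from the 65 and 0.4929 from all 90.
- Baseline as a response without that constraint: baseline-only subjects can shift the estimate (0.27 against 0.35 in that set), but they still add no Week 8 information.

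**Selection bias.** The documents give no removal rates by arm and no correlations, so these are assumptions: 45 per arm, baseline to Week 8 correlation 0.4, 7% random scan loss, and worsening correlated 0.2, 0.3 or 0.5 with activation. There were 3,000 replicates per case, with Monte Carlo error about 0.004.

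| Truth | Removal, placebo / active | Estimate at 0.2 / 0.3 / 0.5 | With imputation using clinical course |
|---|---|---|---|
| 0.50 | 20% / 10% | 0.472 / 0.456 / 0.432 | 0.494 / 0.489 / 0.486 |
| 0 | 10% / 20% | +0.025 / +0.050 / +0.074 | +0.002 / +0.017 / +0.021 |

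In the first row the bias is 0.028 to 0.068 SD; against standard errors of 0.229 to 0.221 that is 0.028/0.229 = 0.12 to 0.068/0.221 = 0.31. With 15% / 10% removal the estimates were 0.486 (correlation 0.2) and 0.462 (0.5). With equal removal of 15% they were 0.502 and 0.495, and with purely random 20% / 10% loss 0.497: no bias beyond simulation error.

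**Estimand.** If 10% or 20% of the active arm stop and the benefit is lost off drug, an on-treatment 0.58 corresponds over all randomised to 0.58 × 0.9 = 0.52 or 0.58 × 0.8 = 0.46.

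**Tipping point** at the two-sided 5% level of 9.1.2, for an observed 0.58, holding the standard error at its complete-case value:

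shortfall in unscanned active subjects = (0.58 − t × SE) / unscanned share of the active arm

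- 9 of 45 unscanned, 36 + 36 scanned, unadjusted: SE = √(1/36 + 1/36) = 0.236 and t × SE = 0.470, so (0.58 − 0.470)/0.20 = 0.55 SD.
- The same with an adjusted SE taken as 0.230: t × SE = 0.459, so (0.58 − 0.459)/0.20 = about 0.61 SD.
- Full loss of benefit in those nine gives 0.58 − 0.20 × 0.58 = 0.464, just below 0.470 and just above 0.459.
- 5 of 45 unscanned, 40 + 36 scanned, unadjusted: SE = 0.230, t × SE = 0.458 and share = 0.111, giving 1.10 SD. With 40 + 40 scanned or an adjusted SE the range runs up to 1.34 SD.

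**The case against.** No method recovers a scan that was never taken, and complete-case ANCOVA is not biased merely because scans are missing. In the checks, loss at random or dependent on baseline gave bias near zero and type I error of 4.7% to 5.3%. An on-treatment estimand is natural for a Phase 2a circuit-engagement question and can be read off the scan schedule. The protocol also plans logistic regressions of discontinuation by arm, records withdrawal reasons, and computes power at 72. All of this stands. It limits the size of the point but does not supply the property claimed in 9.1.2 and 9.2.

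Several stronger readings are tempting and not supported:
- **That no analysis set is stated.** One is: intention-to-treat, 45 and 45. The fault is that it cannot be met for this endpoint.
- **That two primary models compete.** The fMRI paragraph refers forward to the Primary Analysis section, so the mixed model of 9.1.2.1 is the primary one.
- **That the primary test is badly inflated.** Type I error of 10% to 13% appeared only when active-arm subjects were assumed to lose scans according to the unseen Week 8 value; nothing in the documents shows that. Under the clinical-course assumptions, a bias of 0.11 to 0.33 standard errors moves 5% to about 5.1% to 6.3%. If the drug helps, the bias runs toward no effect.
- **That lost scans would overturn a positive result.** Even at nine of 45 with full loss of benefit, the result sits on the boundary. Some of those nine may simply have a poor scan while still on drug.
- **That the SAP is silent.** The supplied SAP text ends in its background section, so its analysis sections cannot be checked.

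**Conclusion.** The point holds for wholly missing Week 8 scans on the primary endpoint. The planned analysis is of randomised subjects with a usable Week 8 scan, and it estimates an on-treatment effect. It is valid if missingness depends only on arm, baseline activation, age, sex and site. The CGI-I removal rule makes dependence on clinical course plausible, and clinical course is not in the model.

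The likely bias is modest, about 0.03 to 0.07 SD at assumed removal of 20% versus 10%, and nil if removal is alike in both arms. The conclusion is sensitive only near the protocol's worst case: the tipping point is 0.55 to 0.61 SD with 9 of 45 active unscanned, against at least 1.1 SD with 5 of 45. These sizes rest on assumed rates and correlations.

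This does not touch SHAPS or other scales measured repeatedly after randomisation, nor a subject who loses only some runs within a session. It should be fixed because the plan states something its design cannot deliver and the remedy is cheap.

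**What to change.** 1. In 9.1.2.1 and 9.2, replace the intention-to-treat and 45-plus-45 wording for this endpoint with: randomised subjects with a usable Week 8 scan, analysed by assigned arm, estimating the on-treatment effect. State the missingness assumption, and extend to this analysis the selection-bias caution that 9.1.2 gives for the completer analysis.
2. Unless the full SAP already has one, prespecify one sensitivity analysis: multiple imputation of missing Week 8 activation from arm, baseline activation, age, sex, site and the last available SHAPS and CGI-S, which are collected at each treatment visit and at withdrawal. Imputation alone still targets the on-treatment effect, so add a delta adjustment for unscanned active subjects, for example 0 to 1 SD below prediction in steps of 0.25. Report the delta at which the two-sided 5% conclusion changes.
3. Beside the planned discontinuation analysis in 9.1.2, tabulate missing or unusable Week 8 scans by arm and reason, including scan quality.

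The cost is wording, one table and one program, with no new visits, scans or patients; the primary estimator is unchanged. The imputation assumptions must be stated, and the imputed standard error is slightly larger (0.23 to 0.24 against 0.22 to 0.23). In the simulations, imputation removed most of the bias but gave no consistent gain in root mean squared error (0.226 to 0.238 against 0.230 to 0.236), so it belongs as a sensitivity analysis and not as the primary.

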9.1.2.1. Primary Analysis

Point estimate and the corresponding confidence interval for the primary study outcome (fMRI ventral striatal activation during reward anticipation of reward during the MID) of

the adjusted predicted score will be obtained. A mixed effects model analysis will be carried out for the primary outcome of the study, task-related fMRI activation in the ventral striatum during anticipation of reward occurring during the Monetary Incentive Delay Task. This analysis will test the hypothesis that CERC-501 will lead to a greater increase in ventral striatal activation during anticipation of reward than placebo.

9.1.2.2. Secondary Analysis

A mixed effects model analysis will also be carried out for the secondary outcomes of the study, SHAPS score and PRT-derived Reward Learning and Response Bias. These analyses will test the hypothesis that CERC-501 will: 1) decrease SHAPS score to a greater degree than PBO; and 2) increase PRT-derived reward learning and response bias to a greater degree than PBO.

9.1.2.3. Exploratory Analysis

Exploratory mixed effects model analyses will also be carried out with the exploratory outcomes of the study. This includes: ventral striatal fMRI activation during anticipation of loss during the MID Task; resting state delta EEG current density in the rostral anterior cingulate; resting state fMRI connectivity; self-rated affective responses to cues and feedback during the MID Task; EEfRT total reward; VAS score; TEPS anticipatory and consummatory pleasure scores; HAM-D score; HAM-A score; CGI-S, CGI-I, and CPFQ score.

9.2. Power Analysis

A total of 90 subjects will be randomized: 45 subjects randomized to CERC-501 and 45 to placebo and included in the primary efficacy analysis. We conservatively anticipate that we will have incomplete data on up to 20% of subjects due to subject drop out or loss of data due to factors such as poor scan quality. As a result, we estimate that we will have complete data on as few as 72 subjects and as many as 90 subjects. In the section above, we outline how we will address the issue of missing data including carrying out analyses on the intent-to-treat (ITT) population and employing mixed effect models. If we assume the worst case scenario of 72 subjects, for a one tailed t-test at an alpha value of 0.05, power is 80% to identify an effect size of 0.58. For a one tailed t-test at an alpha value of 0.10 power is 80% to identify an effect size of 0.50. In Figure 4, it is indicated the effect that could be detected with 80% power at the alpha=0.05 level as a function of number of subjects.

Our capacity to estimate the expected effect size on our primary outcome measure is limited by the studies that have been carried out with this measure to date. The most relevant study was carried out by Stoy and co-workers (2011) who evaluated 15 patients with major depression and 15 controls and administered open-label escitalopram to both groups for 6 weeks and assessed outcome with fMRI activation of the ventral striatum during the MID. However, it must be kept in mind that estimates of power based on this study are likely overly optimistic because this was an open-label treatment study and only included 15 depressed subjects. We can estimate the expected effect size for our study from the ventral striatal activation to reward anticipation subject group by time interaction observed in this study. The effect size for a greater increase in those with depression compared with controls is 0.88. We can also estimate effect size from the pre-

to-post treatment difference in ventral striatal activation during reward anticipation and reward during the MID with fMRI within the depressed group which are 1.1 and 1.0 respectively. These effect sizes suggest that we are likely to have more than sufficient power to detect a significant effect with our primary outcome measure in the proposed study at the alpha=0.05 level with 80% power.

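### The power statements in Section 9.2 are one-tailed, but the protocol plans two-sided tests at 5%: on the same t-test basis, power at 0.58 with 72 subjects is 68%, not 80%

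*Protocol*

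**What the plan says.** Protocol Section 9.1.2 gives the general rule: "Statistical tests will be performed based on a two-sided test at the 5% level of significance". It names no exception. The same section specifies the covariates: "The baseline value of the outcome, centered about its sample mean, will be included in each analysis", together with age and sex. Site is included as well.

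Section 9.1.2.1 specifies a mixed effects model for the primary outcome and states a directional hypothesis: "This analysis will test the hypothesis that CERC-501 will lead to a greater increase in ventral striatal activation during anticipation of reward than placebo". It does not declare a one-sided test.

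Section 9.2 allows for up to 20% incomplete data among 90 randomised subjects: "we estimate that we will have complete data on as few as 72 subjects and as many as 90 subjects". For the lower number it makes two statements that tie a test to a power and a detectable effect, and both are one-tailed. The first is "for a one tailed t-test at an alpha value of 0.05, power is 80% to identify an effect size of 0.58". The second is "For a one tailed t-test at an alpha value of 0.10 power is 80% to identify an effect size of 0.50".

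Figure 4 is introduced as follows: "it is indicated the effect that could be detected with 80% power at the alpha=0.05 level as a function of number of subjects". The text does not say whether that is one- or two-sided, and the figure was not available for this review.

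The section then cites effects of 0.88, 1.1 and 1.0 from an open-label escitalopram study and concludes that power is ample. It also cautions that "estimates of power based on this study are likely overly optimistic because this was an open-label treatment study".

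**The concern.** The two detectable-effect sentences describe tests that the protocol does not plan. For an effect in the expected direction, one-tailed levels of 0.05 and 0.10 correspond to two-sided levels of 10% and 20%. Neither level appears in the analysis section, and the one-tailed 0.10 statement matches no test in the protocol text.

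These sentences tell a reader what the trial can find if the true effect is smaller than in the open-label study. That bears on how a null result is read. Section 1.2.2 says that failing to show an effect on this circuitry would be reasonable grounds for giving up on KOR antagonism in mood and anxiety disorders. Section 9.1.2 also commits to comparing the observed effect and SD with those assumed at planning, so the planning figures will be used again.

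**Working it through.** **Inputs.** 72 or 90 subjects with complete data (Section 9.2). I take equal arms, so n = 36 or 45 per arm. Effect sizes are 0.58, 0.50 and 0.88 (Section 9.2). The planned level is two-sided 5% (Section 9.1.2). The test is an unadjusted two-sample t-test, which is the basis Section 9.2 itself uses.

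**Formulas.** With standardised effect d, the noncentrality is δ = d√(n/2) on 2n − 2 degrees of freedom.

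- One-sided power = P(T′ > t₁₋α)
- Two-sided power = P(T′ > t₁₋α/₂) + P(T′ < −t₁₋α/₂)

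Here T′ is noncentral t with noncentrality δ.

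**Step 1: reproduce the plan's figures (n = 36 per arm, 70 df).**

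- One-sided 0.05, d = 0.58: δ = 0.58 × √18 = 2.461, critical value 1.667, power 78.6%.
- One-sided 0.10, d = 0.50: δ = 0.50 × √18 = 2.121, critical value 1.294, power 79.6%.
- By normal approximation the detectable effects are (1.645 + 0.842) × √(2/36) = 0.586 and (1.282 + 0.842) × √(2/36) = 0.500.

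Both statements agree with 80% to rounding, so the figures do rest on one-tailed tests.

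**Step 2: repeat at two-sided 5%.** With n = 36 the critical value rises to 1.994. With n = 45 (88 df) it is 1.987.

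| Effect | 72 subjects | 90 subjects |
|---|---|---|
| 0.50 | 55.3% | 65.0% |
| 0.58 | 68.0% | 77.7% |
| 0.88 | about 96% | about 98% |
| Detectable with 80% power | 0.67 | 0.60 |

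As a check, the normal approximation (1.960 + 0.842) × √(2/n) gives detectable effects of 0.660 and 0.591. At d = 0.58 it gives power of 69.2% and 78.6%.

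**Step 3: scale.** For 80% two-sided power at 0.58, 48 per arm (96 evaluable) are needed, with power 80.3%; 47 per arm gives 79.5%. The normal approximation, 2 × (1.960 + 0.842)² / 0.58² = 46.7, gives 47 per arm (94). The plan expects 72 to 90. This shows the size of the gap and is not a proposal to change the sample size.

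**Step 4: sensitivity to baseline adjustment.** The documents state neither the baseline-to-Week 8 correlation r nor the SD that standardises 0.58. As an assumption, take the SD to be the unadjusted Week 8 SD and ignore the few degrees of freedom spent on covariates. The effective size is then 0.58/√(1 − r²).

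| Assumed r | Effective d | 72 subjects | 90 subjects |
|---|---|---|---|
| 0 | 0.58 | 68% | 78% |
| 0.3 | 0.61 | 72% | 81% |
| 0.4 | 0.63 | 75% | 84% |
| 0.5 | 0.67 | 80% | 88% |

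If 0.58 is already on the residual scale, adjustment adds nothing and the first row applies.

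**The case against.** The strongest reply is that an unadjusted two-sided t-test is not the planned analysis either. The planned model adjusts for baseline, which can only help materially or leave power about where it is, so 68% is close to a floor. This stands as a limit on the figures. At an assumed correlation of 0.3, power with all 90 subjects passes 80%, and at 0.5 it reaches 80% with 72. But Section 9.2 is itself framed as an unadjusted t-test, so the comparison is like for like, and a possible gain from covariates does not reconcile a one-tailed level with a two-sided rule.

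Second, 0.58 and 0.50 are worst-case detectable effects, while the case for adequate power is argued from 0.88 to 1.1. At 0.88 two-sided power is still about 96% with 72 subjects, so the closing conclusion survives if the true effect is that large. This also stands, and it limits the consequence. However, 0.88 contrasts depressed subjects with controls who all took open-label drug, and 1.1 and 1.0 are pre-to-post changes within one group. None is a drug-versus-placebo effect, and the protocol calls power estimates from that study likely too optimistic.

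Third, the directional hypothesis might be taken to imply a one-sided test. It does not. The secondary hypotheses in Section 9.1.2.2 are directional too, so on that reading the two-sided rule would cover neither the primary nor the secondary outcomes.

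Finally, Figure 4 and much of the SAP were not available. The SAP text that was available ends in its background section and says nothing on test level or power. No claim is made about the unseen parts.

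**Conclusion.** The concern holds, as an inconsistency that should be fixed. The two numerical power statements in the text of Section 9.2 belong to one-tailed tests, while Section 9.1.2 plans two-sided tests at 5%. In the stated worst case the type II error at 0.58 is about 32% rather than 20%, and the detectable effect is 0.67 rather than 0.58. These figures assume equal arms, equal loss in both arms and no covariate adjustment. The analysis rule itself is clear, and power is high if the true effect is near 0.88. What is misstated is the trial's sensitivity to smaller effects.

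**What to change.** Replace the two one-tailed sentences in Section 9.2 with wording such as:

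> For an unadjusted two-sided t-test at the 5% level, 72 evaluable subjects give 80% power for a standardised effect of 0.67 (0.60 with 90). Power at 0.58 is 68% with 72 and 78% with 90. Baseline adjustment may change these figures by an amount that depends on the baseline-to-Week 8 correlation and on the SD used to standardise the effect.

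If the authors have a working value for that correlation, they should state it with the matching SD and give the adjusted figure too. Say whether Figure 4 is one- or two-sided, and redraw it if it is one-tailed. Optionally, qualify the closing claim of ample power by noting that it depends on a true effect near 0.88, and that the three cited effects are not drug-versus-placebo contrasts.

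The cost is protocol wording in one section and possibly one figure. The analysis and sample size do not change. The only downside is a less favourable stated detectable effect.

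### The protocol's claim of ample power rests on effect sizes that are not drug-placebo differences, so the claim is unsupported, though not shown to be false

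*Protocol*

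**What the plan says.** Protocol section 9.2 plans "45 subjects randomized to CERC-501 and 45 to placebo". It expects that "we will have incomplete data on up to 20% of subjects", which leaves "complete data on as few as 72 subjects and as many as 90 subjects". For 72 it gives two detectable effects: "for a one tailed t-test at an alpha value of 0.05, power is 80% to identify an effect size of 0.58", and "For a one tailed t-test at an alpha value of 0.10 power is 80% to identify an effect size of 0.50".

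It then turns to the effect it expects. The source is a study of 15 patients with major depression and 15 controls, which "administered open-label escitalopram to both groups for 6 weeks". From the group-by-time interaction the protocol takes its main figure: "The effect size for a greater increase in those with depression compared with controls is 0.88". It adds two pre-to-post changes within the depressed group, 1.1 for reward anticipation and 1.0 for reward. The closing sentence is: "These effect sizes suggest that we are likely to have more than sufficient power to detect a significant effect with our primary outcome measure".

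Two other places matter:

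- Section 9.1.2.1 (Primary Analysis) tests whether ventral striatal activation rises more on CERC-501 than on placebo. Section 9.1.2 sets all tests at two-sided 5%.
- Section 1.2.2, repeated in SAP section 2.2, says that failing to show an effect on this circuitry, at a dose with acceptable receptor occupancy, would be reasonable grounds to abandon the mechanism for these disorders.

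**The concern.** The study cited for the expected effect has no placebo arm as section 9.2 describes it. The 0.88 is a difference between diagnostic groups that were both on the drug. The 1.1 and 1.0 are uncontrolled changes over time, so they include any regression to the mean, natural recovery or repeat-scan effect along with the drug effect. The trial's placebo arm exists to remove those components.

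The protocol does say that estimates from this study are likely to be over-optimistic. Its two reasons are open-label treatment and the small number of patients. It does not say that the contrast differs from the one the trial tests, and it makes no reduction before concluding that power is ample.

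What is at stake is the reading of a negative result. Section 1.2.2 would count such a result against the whole mechanism, and that inference is only as strong as the trial's power for a plausible drug-placebo effect. In addition, section 9.1.2 (Magnitude of the Clinical Effect) plans to compare the observed effect with the one postulated at the planning stage. The only expected values in section 9.2 come from a different contrast.

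**Working it through.** **Inputs from the protocol.** 36 per arm (72 evaluable) or 45 per arm (90 evaluable); one-tailed 5% and 10% in section 9.2; two-sided 5% in section 9.1.2; cited effects 0.88, 1.1 and 1.0.

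**Formulas.** For n per arm, a standardised difference d and s sides, power = P(T > t[1 − α/s; 2n − 2]), where T is noncentral t with 2n − 2 degrees of freedom and noncentrality d√(n/2). The normal approximation to the detectable effect at 80% power is d = (z[1 − α/s] + 0.842) × √(2/n).

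**1. The protocol's own figures, n = 36, √(2/36) = 0.2357.**

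- One-sided 5%: (1.645 + 0.842) × 0.2357 = 0.586; noncentral t 0.592. Stated: 0.58.
- One-sided 10%: (1.282 + 0.842) × 0.2357 = 0.500; noncentral t 0.503. Stated: 0.50.

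Both reproduce within rounding, and neither uses the cited study.

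**2. Detectable effect under the planned two-sided 5% test.**

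- n = 36: (1.960 + 0.842) × 0.2357 = 0.660; noncentral t 0.670.
- n = 45: 2.802 × √(2/45) = 2.802 × 0.2108 = 0.591; noncentral t 0.597.

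The step from 0.58 to 0.67 at 72 evaluable comes from sidedness alone, which is a separate issue.

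**3. How much of 0.88 must carry over to drug versus placebo for 80% power?**

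- 72 evaluable: 0.592 / 0.88 = 67% (one-sided 5%); 0.670 / 0.88 = 76% (two-sided 5%).
- 90 evaluable, two-sided 5%: 0.597 / 0.88 = 68%.

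**4. Power if the true drug-placebo d takes various values (noncentral t).** The documents give no drug-placebo effect for this measure. Apart from 0.88 (cited) and 0.58 (the stated detectable effect), the values of d are an assumed range; 0.44 is half of 0.88.

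| d | 72, one-sided 5% | 72, two-sided 5% | 90, two-sided 5% |
|---|---|---|---|
| 0.88 | 98% | 96% | 98% |
| 0.58 | 79% | 68% | 78% |
| 0.50 | 68% | 55% | 65% |
| 0.44 | 58% | 45% | 54% |
| 0.40 | 51% | 39% | 47% |
| 0.30 | 35% | 24% | 29% |

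As a further illustration, suppose half of the pre-to-post change of 1.1 would also occur on placebo. That leaves d = 0.55, with power at 72 evaluable of 75% one-sided and 63% two-sided.

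**5. Precision of 0.88.** Read as an independent-groups d with 15 per group (an assumption, because the standardiser is not given), its 95% confidence interval is about 0.12 to 1.62. Even for its own contrast, values well below 0.58 are not excluded.

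**The case against.** The protocol is fairly open. It says that its ability to predict the effect is limited, calls estimates from this study too favourable, and labels each figure for what it is. The conclusion is hedged, and it is arithmetically right if 0.88 applies. The detectable effects do not depend on the cited study, so removing the sentence changes no sample size, test or endpoint. Section 9.1.2.1 also requires a point estimate with a confidence interval, which limits how far a negative result can be over-read. All of this stands. It does not rescue the conclusion, which is drawn directly and undiscounted from figures just described as too favourable, and the mismatch of contrast is not among the reasons given.

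A reader might go further and infer that the trial is underpowered. The documents do not support that:

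- The true drug-placebo effect is unknown, and 0.3 to 0.5 is an assumption. A low range produces low power by construction.
- The direction of any bias in 0.88 is unknown. Section 8.4.1 says that depressed patients start with reduced activation, so regression to the mean or recovery could inflate the interaction. Subtracting the change in controls who also took the drug could shrink it.
- Section 9.1.2 puts the baseline value, age, sex and site in the model. If baseline and week 8 correlate at 0.3, 0.5 or 0.7 (assumed), multiplying 0.67 by √(1 − r²) gives a detectable d of about 0.64, 0.58 or 0.48 in raw standard-deviation units. So 0.67 is the figure for an unadjusted test, not a floor.

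A reader might also infer that no drug-placebo estimate for this measure exists. That would be a claim about the literature. Section 8.4.1 mentions a placebo-controlled study in healthy controls, but section 9.2 takes no effect size from it.

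**Conclusion.** The point holds as an unsupported claim. None of 0.88, 1.1 and 1.0 estimates the drug-placebo difference that the trial tests, so they cannot establish ample power. The conclusion requires about two-thirds (one-sided 5%) to three-quarters (two-sided 5%) of 0.88 to carry over when 72 are evaluable, and the protocol offers no argument that it would. The point does not depend on sidedness: over the assumed range d = 0.3 to 0.5 with 36 per arm, power is 35% to 68% one-sided and 24% to 55% two-sided. These figures rest on an unadjusted two-sample t-test, equal arms, and cited effects expressed on the between-subject standard-deviation scale.

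The sample-size arithmetic itself is sound, and inadequate power has not been shown. The matter deserves correction mainly because section 1.2.2 would treat a negative result as grounds to drop the mechanism.

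**What to change.** In protocol section 9.2:

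1. Delete the closing sentence that claims ample power.
2. State that 0.88 is a patient-versus-control interaction with both groups on the same drug, that 1.1 and 1.0 are uncontrolled within-patient changes, and that the protocol gives no drug-placebo estimate for this measure in patients.
3. Express power as a detectable effect under the two-sided 5% test of section 9.1.2: d of about 0.67 with 72 evaluable and 0.60 with 90, for an unadjusted t-test. Note that baseline adjustment may lower these values, and that the move from 0.58 to 0.67 reflects sidedness.
4. If power at smaller effects is shown, label it as an assumed range.

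The cost is wording only, with no change to sample size or conduct; the stated power becomes less favourable. The SAP text supplied ends with the rationale, so any sample-size section there should be checked and aligned.
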